6 DEMOGRAPHICS AND OTHER BASELINE CHARACTERISTICS

Unless otherwise specified, all summaries will be based on the SS and repeated on the RS (unless the SS and RS analysis sets are identical) and on the ATS.

6.1 Demographics

The following demographic variables measured at Baseline will be summarized overall and by treatment group: age (years), gender, country, geographic region, country, race, ethnicity, height (cm), body weight (kg) and Body Mass Index (BMI) (kg/m²).

Age, body weight and BMI will be summarized as continuous variables and as categorical variables based on the categories specified below.

For age, 3 sets categories will be defined:

- ≤ 18 , 19 to < 65 , ≥ 65 years (clinicaltrials.gov requirement),
- 18 to < 65 , 65 to < 85 , ≥ 85 years (EudraCT requirement),
- 18 to < 45 , ≥ 45 to < 65 , ≥ 65 years.

For body weight, categories will be: ≤ 100 kg, > 100 kg.

BMI (in kg/m^2) will be recalculated during analysis based on height (in meter) and weight (in kg). The formula for BMI (kg/m^2) calculation is:

$$BMI = \frac{\text{Body weight (kg)}}{(\text{Height(m)})^2}$$

For BMI, categories will be: < 25 , 25 to < 30 , 30 to < 35 , ≥ 35 kg/m^2 .

A separate frequency table will summarize the subject's lifestyle on the SS.

By-subject listings on demographics, female subject's childbearing potential data will be provided for all screened subjects. Listing on lifestyle will be provided on the RS.

To understand the study population during the different periods of the COVID-19 pandemic, the reporting of Baseline demographics will be repeated by COVID-19 pandemic period (pre or during as determined by the Baseline visit date) on the SS.

6.2 Baseline characteristics

6.2.1 Baseline values for components of the primary efficacy variable

Baseline values for the 7 components of the primary efficacy variable will be summarized by treatment group and overall. The following variables will be summarized:

- TJC
- SJC
- PGA-PsA
- PhGA-PsA
- PtAAP
- HAQ-DI
- hs-CRP (mg/L).

For hs-CRP, SJC and TJC, the following rule will be applied: if the Baseline value is missing, then the most recent value (taken at previous unscheduled visit or at Screening) will be considered. If the value is still missing, the Baseline value will be considered missing.

The hs-CRP variable will be summarized using descriptive statistics and in classes (≥ 6 mg/L, < 6 mg/L).

Efficacy variables not listed above will not be presented in the Baseline characteristics section. They will be presented in by-visit tables in the context of the analysis of secondary and other efficacy variables.

To understand the study population during the different periods of the COVID-19 pandemic, the reporting of Baseline characteristics will be repeated by COVID-19 pandemic period (pre or during as determined by the Baseline visit date) on the SS.

6.2.2 Other Baseline characteristics

The following variables will be summarized by treatment group and overall:

- Bone erosion (0, ≥ 1) – based on IXRS randomization strata
- Bone erosion (0, ≥ 1) – based on actual randomization strata (as per imaging data)
- Bone erosion (≥ 1) and/or hs-CRP ≥ 6 mg/L at Screening (Yes, No). To determine this, bone erosion will be derived from imaging data and corresponds to actual randomization strata
- % of BSA affected by PSO (<3%, $\geq 3\%$ to $\leq 10\%$, $>10\%$)
- PASI score at Baseline (for subjects with PSO involving at least 3% of BSA at Baseline). This variable will be summarized as a continuous variable and in classes (<10, 10 to 20, >20)
- BASDAI (<4, ≥ 4)
- Rheumatoid factor (positive, negative). A rheumatoid factor value <30 IU/mL is defined as negative and a value ≥ 30 IU/mL is defined as positive
- Anti-cyclic citrullinated peptide (CCP) antibodies (positive, negative). Anti-CCP antibodies negative is a value <20 U/mL and a value ≥ 20 U/mL is defined as positive
- Nail psoriasis (yes, no)
- Dactylitis (“yes” if LDI score >0 , “no” if LDI score = 0, missing)
- Enthesitis based on LEI (“yes” if LEI score >0 , “no” if LEI score = 0, missing)
- Enthesitis based on SPARCC (“yes” if SPARCC >0 , “no” if SPARCC = 0, missing)
- Prior NSAID (yes, no)
- NSAID at Baseline (yes, no)
- Past cDMARDs therapy (yes, no)
- Prior cDMARDs (0, 1, ≥ 2) ([Section 4.8](#))
- cDMARDs at Baseline (yes, no)
- HLA-B27 (positive, negative)
- Methotrexate at Baseline (yes, no) ([Section 4.8](#))
- Prior oral corticosteroids (yes, no)
- Oral corticosteroids at Baseline (yes, no).

To understand the study population during the different periods of the COVID-19 pandemic, the reporting of other Baseline characteristics will be repeated by COVID-19 period (pre or during as determined by the Baseline visit date) on the SS.

6.2.3 History of psoriatic arthritis

The following PsA history variables will be summarized overall and by treatment group:

- The time since first diagnosis of PsA (years). Time since first diagnosis will be summarized as a continuous variable and as categorical variables based on following categories: <1, 1-<2, ≥ 2 years
- The time since first diagnosis of PSO (years), calculated as :

$$\frac{\text{Date of informed consent} - \text{Date of diagnosis}}{365.25}$$

If the date of diagnosis is partial, it should be imputed to the most recent feasible date (ie, last day of the month if only day is missing, or the last day of the year if day and month are missing).

- The age at first diagnosis date of PsA (years), calculated as:

$$\frac{\text{Date of PsA diagnosis} - \text{Date of birth}}{365.25}$$

If the date of PsA diagnosis is partial, it should be imputed to the most recent feasible date (ie: the last day of the month if only day is missing, or the last day of the year if day and month are missing. Partial date should not be imputed later than the subject's screening date). For subjects enrolled at German sites, only the year of birth may be entered into the eCRF for this study. For these subjects age will be calculated after imputing their date of birth to be on January 1st.

- The PsA subtype (polyarticular – symmetric arthritis, oligoarticular – asymmetric arthritis, distal interphalangeal, joint predominant, spondylitis predominant, arthritis mutilans)

The data on history of psoriasis and psoriatic arthritis will be listed for all screened subjects.

6.3 Medical history and concomitant diseases

Medical history conditions are defined as conditions that have resolved prior to study entry.

Ongoing medical conditions are defined as conditions that are ongoing at the time of study entry.

- Medical history and ongoing medical conditions will be summarized on the SS by MedDRA System Organ Class (SOC) and Preferred Term (PT), by treatment and overall including the number and percentage of subjects with each condition. The denominator of the percentages will be the number of subjects in the population considered. The tables will be ordered alphabetically for SOC and in terms of decreasing frequency for PT within SOC in the BKZ treatment group. In the event of ties, PT will be ordered alphabetically.

Medical history and ongoing medical conditions will be listed by treatment and subject including the reported term, PT, and SOC on the RS. The start date (month and year only) and the end date (or ongoing if applicable) will be included in the listing. Partial dates will not be imputed. A glossary of all medical history conditions will be presented including the reported term, PT and SOC. Concomitant medical procedures will be listed on the RS.

6.4 Prior and concomitant medications

Prior medications include any medications that started prior to the date of the first IMP administration.

Concomitant medications are medications taken at least one day in common with the IMP dosing period.

The IMP dosing period corresponding to the combined DBP and ATP will be calculated as follows:

The study medication dosing period start date is defined as the date of first dose.

The study medication dosing period stop date is defined as follows:

- For subjects who are ongoing at the time of the clinical data cut (not including participants who are in SFU) use date of last clinical contact
- For subjects who died prior to last visit (not including those who died during SFU), use the minimum of the following:
 - Date of death
 - Date of last dose of any study medication + 28 days
- For subjects who complete the study as planned, the dosing period ends at the later of the following 2 dates:
 - Date of last administration of IMP + 14 days
 - The last scheduled visit date not including SFU
- For all other subjects, use the maximum of the following:
 - Date of last dose of any study medication + 28 days
 - Date of last visit (not including SFU).

In the case of missing data, the classification of medications as prior or concomitant will be performed as described in [Section 4.2.4](#). Imputations of missing data will be performed before calculation of relative study days.

The number and percentage of subjects taking prior medications (excluding past psoriasis medications) will be summarized on the SS by treatment group, overall and by ATC class, presenting Anatomical Main Group (ATC Level 1), Pharmacological Subgroup (ATC level 3) and PT.

The table summary will be ordered alphabetically for the ATC class and in terms of decreasing frequency for PT within ATC class in the BKZ treatment group. In the event of ties, PT will be ordered alphabetically.

The number and percentage of subjects taking concomitant medications will be summarized similarly on the SS by treatment group (for the Week 24 analysis on the period from Baseline to Week 24, for the Week 52 analysis on the overall study treatment period).

A by-subject listing of all prior (on the RS) and concomitant medications (on the RS) as well as glossary of all medical medications will be provided.

6.5 Prohibited medications and permitted rescue therapy after Week 16

Prohibited or restricted medications are defined in the protocol (section 7.8.2). Prohibited medications will be listed on the SS.

Some permitted rescue therapies are allowed after Week 16 as defined in Section 5.4 of the protocol.

The number and percentage of subjects who used permitted rescue medications after Week 16 will be summarized by ATC class, presenting ATC Level 1, ATC level 3, and PT. This table will be produced on the ATS.

Permitted rescue therapies will be listed on the SS.

7 MEASUREMENTS OF TREATMENT COMPLIANCE

Treatment compliance summaries will be provided:

- On the SS for the DBP, by randomized treatment and for all subjects.
- On the ATS for the ATP, by randomized treatment, for all BKZ treated subjects and for all subjects
- On the AMS for the AMP, by randomized treatment, for all BKZ treated subjects and for all subjects.

Due to the method of IMP administration, compliance will be examined in terms of completed injections. Treatment compliance will be calculated as:

$$\frac{\text{Total number of actual (completed) injections}}{\text{Total number of expected injections}} \times 100 \%$$

The total number of expected injections is derived relative to when the subject finishes treatment:

- If a subject completes the DBP, 8 injections are expected (every 2 weeks from Baseline to Week 16)
- If a subject completes treatment over the entire study, 26 injections are expected (every 2 weeks from Baseline to Week 50)
- If a subject discontinues early, then the number of expected injections is based on the time of early discontinuation relative to the dosing visits. This number will be calculated by determining the number of expected dosing visits prior to the date of early discontinuation. If the early discontinuation coincides with an expected dosing visit, this visit will be used to determine the number of expected injections.

A summary of percent treatment compliance categorized as <75% and $\geq 75\%$ will be provided by treatment group, as well as a by-subject listing of treatment compliance.

8 EFFICACY ANALYSES

8.1 Statistical analysis of the primary efficacy variable

8.1.1 Derivation of ACR50 response

The ACR50 response at Week 16 is the primary efficacy variable.

This is a composite endpoint that represents at least 50% improvement from Baseline at Week 16 for each of the following:

- TJC (based on 68 joints),
- SJC (based on 66 joints),
- At least 3 of the 5 remaining core set measures:
 - PGA-PsA
 - PhGA-PsA
 - PtAAP
 - HAQ-DI
 - hs-CRP.

Prior to deriving ACR50, the percent of change for each component will be calculated as:

$$\text{Percent improvement from Baseline} = 100 \times \frac{\text{Baseline Value} - \text{Week 16 value}}{\text{Baseline Value}}$$

As the ACR response is based on 7 different component scores, it is necessary to consider various data scenarios that could impact the calculation of ACR response. The rules described here are applicable in the context of the calculation of ACR response and may differ from the rules applied for calculating and summarizing the components individually (some values may need to be imputed for component analysis but are not required here to evaluate the ACR response)

The following rules will be applied prior to invoking any imputation analysis at the variable level:

- If a subject has a component value that is equal to 0 at Baseline and the post-Baseline value is ≥ 0 , then the percent improvement for that component will be treated as 0 for purposes of ACR response calculations.
- If a subject has a component value that is missing at Baseline, then the percentage of improvement for that component will be treated as missing for purposes of ACR response calculations.

Observed data will be used to calculate ACR response where possible. In case of partial missing data where an observed response may be calculated, imputed data will not change the result.

To address possible missing data in ACR components, ACR50 will be derived as below:

- Positive response on ACR50:

- Improvement at Week 16 of at least 50% from Baseline on SJC and TJC and at least 3 out of the 5 remaining ACR components (regardless of whether the 2 remaining components are missing or not).
- Negative response on ACR50:
 - No improvement at Week 16 of at least 50% from Baseline on SJC (regardless of whether the remaining components are missing or not).
 - No improvement at Week 16 of at least 50% from Baseline on TJC (regardless of whether the remaining components are missing or not).
 - No improvement for at least 3 out of the 5 following ACR components (PGA-PsA, PhGA-PsA, PtAAP, HAQ-DI, hs-CRP) regardless of whether the remaining components are missing or not.
- Missing ACR50 response:
 - For all other situations that are not specified above.

For the OC analysis ([Section 8.1.4.6](#)): if a given visit date falls after the treatment discontinuation date, the endpoint at this visit and all subsequent visits (whether the data were observed or not) will be derived but reported as missing.

For the MI analysis ([Section 8.1.4.3](#)): If a given visit date falls after the treatment discontinuation date, the endpoint at this visit and all subsequent visits (whether the data were observed or not) will be imputed. Responses falling after an IE (defined as treatment discontinuation due to AE or lack of efficacy for the modified composite estimand) will be set to non-response.

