For subjects who switch treatment from placebo to BKZ at Week 16 (Visit 10), an additional Baseline value (called Week 16 Baseline) will be defined for efficacy variables. The Week 16 value will be considered as the Baseline value regardless of whether the Placebo subjects switched to BKZ on a later visit.

The variables listed below will be analyzed relative to the Week 16 Baseline value for the ATP, for timepoints after Week 16:

- PASI90 response
- ACR50 response.

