8.3.1.2 ACR20, ACR50 and ACR70

Method for derivation of ACR50 can be found in [Section 8.1.1](#). ACR20 and ACR70 will be derived similarly except that they will be based on a 20% and on 70% improvement from Baseline.

ACR20, ACR50 and ACR70 responses will be analyzed at Week 2, 4, 8, 12, 16, 20, 24, 28, 32, 36, 44, 52.

For the placebo group, ACR50 response will be presented both based on the Day 1 Baseline and on the Week 16 Baseline (on the ATS, for the ATP, for subjects switching to BKZ at Week 16).

8.3.1.3 PASI75, PASI90 and PASI100 response (in subjects with PSO involving at least 3% of BSA at Baseline)

Method for derivation of PASI score can be found in [Section 8.2.1.2](#).

PASI75, PASI90, PASI100 are binary variables equal to 1 if the percentage improvement from Baseline in the PASI scores is $\geq 75\%$, $\geq 90\%$, 100% and 0 if the percentage improvement from Baseline is $< 75\%$, 90%, 100%.

PASI75, PASI90, PASI100 as well as the PASI score and the change from Baseline for subjects with PSO involving at least 3% of BSA at Baseline will be analyzed at Week 2, 4, 8, 12, 16, 20, 24, 28, 32, 36, 52.

For the placebo group, PASI90 responses will be determined both based on the Day 0 Baseline and on Week 16 Baseline (on the ATS, for the ATP, for subjects switching to BKZ at Week 16).

8.3.1.4 Composite endpoints composed of ACR50 and PASI90 and ACR50 and PASI100 responses (subjects with PSO involving at least 3% of BSA at Baseline)

The composite endpoint composed of ACR50 and PASI90 is a binary variable equal to 1 for subjects responding to ACR50 (ACR50=1) and PASI90 (PASI90=1).

The composite endpoint will be equal to 0 if ACR50=0 or PASI90=0 regardless of whether any of the 2 endpoints is missing.

The same rules as above will be applicable for the composite endpoint on ACR50 and PASI100.

The composite endpoints will be missing if both endpoints are missing or if any of the 2 is missing and the other one equal to 1.

Each endpoint (ACR50 and PASI90 or PASI100) will be imputed separately before deriving the composite endpoint.

The composite endpoints for subjects with PSO involving at least 3% BSA at Baseline will be analyzed at Week 2, 4, 8, 12, 16, 20, 24, 28, 32, 36, 52.

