- The mean proportion of responders in the multiple imputed datasets and the 95% CI (modified composite estimand). For ACR50 response at post-Week 16 visits for subjects responding at Week 16, the same imputed data as generated in the context of the analysis of the primary efficacy endpoint will be used.
 - For enthesitis and dactylitis free-state based on the pooled data of PA0010 and PA0011 subjects (for subjects in the BKZ 160mg Q4W and the Placebo group), the MI will be performed on the pooled dataset (using data from Baseline, Week 4, 8, 12 and 16) the same way as described in [Section 4.2.2.2](#), but with the following covariates in that order for each SAS® PROC MI: region (North America, Western Europe and Eastern Europe in that order) and study-id (“1” for PA0011 and “0” for PA0010).
 - For enthesitis based on LEI, the MI will be run on all subjects and results reported for subjects with LEI>0 at Baseline ; for other binary variables derived from continuous value(s), the MI will be run on the subset of subjects (if applicable) for which the variable will be reported (ie: for LDI and Tender dactylitis count in the context of PASDAS calculation, on subjects with LDI>0 at Baseline)
 - For ACR50 based on Week 16 Baseline, the MI will be run on Week 16 and post-week 16 values, on the ATBS for the Placebo group. Week 16 value will be considered as the Baseline value regardless of whether the Placebo subjects switched to BKZ on a later visit.
 - For PASI90 based on Week 16 Baseline, the MI will be run on W16 and post-week 16 values, on the ATBS for the Placebo group on subjects with PSO involving at least 3% of BSA at Week 16. Week 16 value will be considered as the Baseline value regardless of whether the Placebo subjects switched to BKZ on a later visit.
- The observed number and proportion of responders on subjects with observed data

For categorical endpoints (ie, EQ-5D-3L dimensions score, DAPSA state, PASDAS categories) using:

- The number and percentage by endpoint category using the NRI approach (as performed for the primary analysis of the primary endpoint with the exception that the NRI is replaced by the worst category imputation)

- The mean percentage and corresponding 95% CI by endpoint category in the multiple imputed datasets (modified composite estimand). Regardless of imputed values, the value of the categorical endpoint after IE are by default set to the worst category (ie: High Disease Activity for DAPSA state)

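### ACR50 measured from the Week 16 Baseline includes placebo switchers who cannot respond by construction, because a zero joint count at Week 16 fixes a mandatory component at 0% improvement

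*SAP*

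**What the plan says.** Section 3.3 defines a second Baseline for placebo subjects who move to bimekizumab at Week 16: "The Week 16 value will be considered as the Baseline value regardless of whether the Placebo subjects switched to BKZ on a later visit". It applies this to two endpoints, PASI90 and ACR50: "The variables listed below will be analyzed relative to the Week 16 Baseline value for the ATP, for timepoints after Week 16".

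Section 8.3.1.2 refers back to Section 8.1.1 for the derivation and adds: "For the placebo group, ACR50 response will be presented both based on the Day 1 Baseline and on the Week 16 Baseline". The second version is reported on the Active Treatment-Blind Set.

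Section 8.1.1 computes percent improvement as the drop from Baseline divided by the Baseline value, and has a rule for a zero denominator: "If a subject has a component value that is equal to 0 at Baseline and the post-Baseline value is" at or above 0, "the percent improvement for that component will be treated as 0 for purposes of ACR response calculations". Both joint counts are mandatory. Either of these alone makes ACR50 negative: "No improvement at Week 16 of at least 50% from Baseline on SJC (regardless of whether the remaining components are missing or not"), and "No improvement at Week 16 of at least 50% from Baseline on TJC (regardless of whether the remaining components are missing or not").

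Section 8.3.2.2 describes the multiple imputation for this version: "For ACR50 based on Week 16 Baseline, the MI will be run on Week 16 and post-week 16 values", on the placebo group of that analysis set, with no condition on joint counts. The next bullet, for PASI90 from the Week 16 Baseline, limits the analysis to subjects with at least 3% of body surface area affected at Week 16.

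**The concern.** The zero rule was written for the Day 1 Baseline, where it hardly touches the joint counts: Section 2.3.1 requires TJC and SJC of at least 3 for entry. Nothing carries that floor to Week 16. A placebo subject may have lost all swollen or all tender joints by then, and the rule then governs every later visit.

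The table is there to show ACR50 response after starting bimekizumab. As written, its denominator includes subjects for whom no later joint count could give a response, and the reader is not told how many. The same person can be a responder in the Day 1 version and a non-responder in the Week 16 version at the same visit, with no worsening at all.

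**Working it through.** **Inputs.** The zero rule and the two mandatory joint criteria come from Section 8.1.1, the Week 16 Baseline from Section 3.3, the population from Sections 8.3.1.2 and 8.3.2.2, and the entry floor of 3 joints from Section 2.3.1. For illustration only: the planned placebo arm of 280 (Section 2.3.1) and the 43.8% ACR50 rate used in the sample-size section (2.4.1). The share f of switchers with SJC=0 or TJC=0 at Week 16 is not in the SAP and is assumed. The SAP states no figure that depends on this rule, so there is none to reproduce.

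**Step 1: the rule.** Improvement = 0 if Baseline = 0; otherwise 100 × (Baseline − later value) / Baseline. ACR50 needs at least 50% on TJC, at least 50% on SJC, and at least 50% on 3 of the 5 other components. Suppose all 5 others have improved enough:

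| Week 16 TJC / SJC | Later TJC / SJC | TJC improvement | SJC improvement | ACR50 |
|---|---|---|---|---|
| 4 / 4 | 2 / 2 | 50% | 50% | yes |
| 4 / 4 | 0 / 0 | 100% | 100% | yes |
| 4 / 0 | 0 / 0 | 100% | 0% | no |
| 0 / 4 | 0 / 0 | 0% | 100% | no |
| 0 / 0 | 0 / 0 | 0% | 0% | no |

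Going through the possible later joint counts (TJC 0 to 68, SJC 0 to 66) with either Week 16 count at zero gives no case of response.

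**Step 2: the same subject on the Day 1 Baseline.** With the entry minimum of 3 on each count and 0 afterwards, improvement is 100 × (3 − 0) / 3 = 100% on both. The subject is a responder if 3 of the other 5 components also reach 50%.

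**Step 3: missing-data handling.** The derived value is a definite negative, not a missing one, so it stands under NRI, MI and observed cases. The exception is observed-case visits after treatment discontinuation, which are reported as missing. If the zero rule were read as applying to Day 1 only, the formula would divide by zero and the joint component could not be derived. Section 4.2.2.1 then imputes non-response, so the NRI result is the same.

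**Step 4: size.** If p is the response rate among switchers with both counts above zero, the reported rate is (1 − f) × p, with a ceiling of 1 − f.

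| Assumed f | Subjects of 280 | Ceiling | Reported rate when p = 43.8% | Difference |
|---|---|---|---|---|
| 5% | 14 | 95% | 0.95 × 43.8 = 41.6% | 2.2 points |
| 10% | 28 | 90% | 0.90 × 43.8 = 39.4% | 4.4 points |
| 20% | 56 | 80% | 0.80 × 43.8 = 35.0% | 8.8 points |

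**The case against.** The strongest reply is about the target. If the quantity is the proportion of all switchers who gain a further 50% from their Week 16 state, a subject with no swollen joints has no such gain to make, and non-responder is the right label. The zero rule is an explicit convention, and improvement from zero has no natural value. This stands in part: the rule is not an arithmetic error. It does not remove the difficulty that a rate presented as response after the switch contains subjects who could not respond, in unknown number.

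The reply is also right that the stakes are low. The table is an extra, exploratory, single-group summary in Table 4-4. It is outside the hierarchy in Table 4-5, and a subject who stays clear can still count as a responder in the Day 1 version.

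The contrast with PASI90 is weaker than it looks. PASI responses are defined in a body-surface subset at Day 1 too, so the Week 16 condition moves an existing subset to the new Baseline. ACR50 has no subset to move. The contrast shows that a Week 16 disease condition is workable here, not that the SAP contradicts itself.

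A reader might go further and infer three things that the SAP does not support:

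- **That a sizeable group must be affected, because 16% placebo ACR50 is assumed at Week 16.** ACR50 needs a 50% reduction, not a count of zero, so f does not follow from the 16%.
- **That the true post-switch rate is understated by the amounts in the table above.** The 43.8% is a Week 12 median over three dose groups in another study, and 280 is the planned number randomized, not the number who switch. The figures only show how (1 − f) × p behaves.
- **That the entry threshold of 3 should be reimposed at Week 16.** Counts of 1 or 2 allow a computable 50% improvement (1 to 0, 2 to 1). That cut-off would drop evaluable subjects and would not match the calculation, which removes zero counts only.

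**Conclusion.** The point holds for one exploratory analysis. In the by-visit ACR50 table from the Week 16 Baseline, every placebo switcher with a zero swollen or tender joint count at Week 16 is a non-responder at all later visits, whatever happens on treatment, and the reported rate is capped at 1 − f. That follows from the SAP's rules with no numerical assumption. The size cannot be determined: f is not given, and the 2.2 to 8.8 points rest on an assumed f of 5% to 20% and a borrowed 43.8%. The primary analysis from Day 1 is essentially untouched because of the entry floor, and no hypothesis in the testing sequence uses this table. This is a cheap improvement, not a threat to the trial's conclusions.

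**What to change.** In Sections 8.3.1.2 and 8.3.2.2, restrict ACR50 based on the Week 16 Baseline to placebo switchers with TJC>0 and SJC>0 at Week 16. Report beside the table how many were excluded for a zero count. Keep the Day 1 Baseline analysis in all subjects, so that those who reached zero on placebo and stayed there remain visible. The cost is one sentence in each section, one subset flag, and a slightly smaller denominator in an exploratory table. The table covers a single group, so selecting on a Week 16 value breaks no randomized comparison.
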